8.6.4. Follicle Stimulating Hormone

Follicle stimulating hormone (FSH) will be performed at Screening and only needed if claiming exemption from contraception requirement due to menopause.

FSH results will be presented in a data listing.

8.6.5. Discussion/Documentation of Contraception Method

Discussion/documentation of contraception method will be performed at Screening and Check-in for each period. The discussion/documentation of contraception method results will be kept in the source documents and will not be recorded on the CRF; therefore, the discussion/documentation of contraception method results will not be presented in any of the tables, listings, or figures.

8.6.6. Retained Sample

A single 12 mL sample will be retained for evaluation in the event of an unexpected safety finding. The retained serum sample will only be collected pre-dose on Day 1 of Period 1.

Retained sampling results will be presented in a data listing.

9. Pharmacokinetics and Pharmacodynamic Analysis

9.1. Pharmacokinetic Sampling

Whole blood samples will be collected for the measurement of plasma concentrations of total molybdenum, PUF molybdenum, bupropion and hydroxybupropion at the following time points: pre-dose and post-dose at 1, 2, 3, 4, 5, 6, 8, 12, 24, 48, 72, 96, 120, 144, 168, 192, 216, 240, and 336 hours in each period. Additional samples may be collected at additional time points during the study if warranted and agreed upon between the Investigator and Alexion. Collection of samples for PK evaluation should occur as close as possible to the scheduled time and actual time of collection should be documented on the eCRF. Samples collected within $\pm 10\%$ of the scheduled time, or 30 minutes, whichever is less, will not be considered a protocol deviation. In the event of a safety occurrence and after agreement between the Investigator and Medical Monitor, up to 3 additional PK sampling timepoints may be added.

PK samples will also be used for the PD analysis of total copper and PUF copper.

9.2. Below the Limit of Quantification Values / Missing Values

For PK and the PD measure plasma total copper parameter calculations, concentrations below the limit of quantification (BLQ) prior to the first measurable concentration will be set to zero; all other BLQ values will be treated as missing. For PUF copper parameter calculations, all BLQ values will be set to zero.

For PK and PD concentration summaries, BLQ values will be set to zero.

9.3. Pharmacokinetic/Pharmacodynamic Data Presentation Conventions

PK and PD concentration data will be summarized using descriptive statistics (number of participants (N), number of participants with available data (n), arithmetic mean, SD, arithmetic CV, geometric mean (GM), geometric CV, median, minimum and maximum).

The predose PD concentration will be used as baseline; absolute change from baseline will be calculated as: a postdose concentration value – baseline concentration value; percent change from baseline will be calculated as: ([a postdose concentration value – baseline concentration value] / baseline concentration value) $\times 100\%$.

The following conventions will be applied to PK/PD presentations and summaries.

• For continuous variables, all mean and median values are formatted to one more decimal place than the measured value. Standard deviation values are formatted to two more decimal places than the measured value. Minimum and maximum values are presented with the same number of decimal places as the measured value.

• Date variables are formatted as DDMMMYYYY for presentation. Time is formatted in military time as HH:MM for presentation.

9.4. Pharmacokinetic Parameters

The following plasma PK parameters will be calculated for total molybdenum, PUF molybdenum, bupropion and hydroxybupropion using noncompartmental methods with Phoenix[®] WinNonlin[®] (Certara USA Inc., Princeton, New Jersey) Version 8.0 or higher or SAS Version 9.4 or higher (SAS Institute Inc., Cary, North Carolina), as applicable. It is expected that in Treatment B the dosing of ALXN1840 and bupropion will occur at the same time. Calculations will be based on the actual sampling times relative to the actual reference ALXN1840 or bupropion dosing times recorded during the study.

- T_{lag}: time delay between the time of dosing and time of appearance of drug concentration in plasma (for plasma total molybdenum and PUF molybdenum with ALXN1840 administration)
- C_{max}: maximum observed concentration in plasma
- T_{max}: time to reach maximum observed concentration in plasma
- AUC_t: AUC from time 0 to the last quantifiable concentration, calculated using the linear trapezoidal rule
- AUC_{∞} : AUC versus time curve from time 0 to infinity, calculated using the linear trapezoidal rule
- % AUC_{extrap}: AUC extrapolated from time t to infinity as a percentage of total AUC $_{\infty}$
- $t_{1/2}$: terminal elimination half-life
- λ_z : apparent terminal-phase elimination rate constant

For ALXN1840, equivalent molybdenum dose will be used to calculate total molybdenum (and PUF molybdenum if applicable) CL/F and V_d/F values: molybdenum MW of 95.95 Da/ALXN1840 MW of 432.54 Da \times 60 mg ALXN1840 = 13.31 mg molybdenum dose. For bupropion, 150 mg dose will be used for the calculation.

- CL/F: apparent oral clearance
- V_d/F: apparent volume of distribution

For hydroxybu propion, metabolite to parent ratios will be reported for C_{max}, AUC_t and $AUC_{\infty}.$

Additional plasma PK parameters may be calculated if deemed appropriate.

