1. PROTOCOL SUMMARY

1.1. Synopsis

Protocol Title: A Phase 1, Randomized, 2-Period, 2-Sequence, Cross-over Study to Determine the Effect of ALXN1840 on the Metabolism of a CYP2B6 Substrate in Healthy Participants.

Short Title: Phase 1 Study of ALXN1840 on the Metabolism of a CYP2B6 Substrate in Healthy Participants.

Rationale:

ALXN1840 is considered to have potential for weak to moderate drug-drug interactions (DDI) due to inhibition of cytochrome P450 2B6 (CYP2B6) according to in vitro studies using human liver microsomes and simulations performed to assess the potential for DDI risks. This study has been designed to determine the effect of ALXN1840 enteric-coated (EC) tablets at a single dose of 60 mg (4 × 15 mg), on the metabolism of bupropion (bupropion hydrochloride [HCI], WELLBUTRIN SR), a sensitive CYP2B6 substrate, at a single dose of 150 mg. A single dose of 60 mg ALXN1840 as a perpetrator is considered appropriate due to lack of potential for time-dependent inhibition (TDI) under the maximum observed ALXN1840 concentration in plasma after repeated daily dosing at steady state. A single dose of 150 mg bupropion is considered appropriate due to its linear pharmacokinetics (PK) within the approved therapeutic dose range.

The 60 mg dose of ALXN1840 is the maximum allowed daily dose in the on-going Phase 3 Study WTX101-301 in patients with Wilson disease (WD). The 150 mg bupropion single dose has been selected based on the WELLBUTRIN SR United States Prescribing Information (USPI) (WELLBUTRIN SR) as it has limited safety concerns (such as seizure).

Objectives and Endpoints

Objectives	Endpoints
Primary	
To determine the effect of ALXN1840 on the PK of bupropion, a sensitive CYP2B6 substrate	• PK parameters of bupropion (maximum observed plasma concentration [C _{max}], area under the plasma concentration (AUC) versus time curve from time 0 to the last quantifiable concentration [AUC _t], and AUC versus time curve from time 0 to infinity [AUC _∞]) with and without the coadministration of ALXN1840
Secondary	

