Pharmacokinetic parameters derived from plasma concentrations of total Mo, bupropion and hydroxybupropion will be presented in data listings and summarized separately using the following descriptive statistics: number of participants, arithmetic mean, SD, arithmetic CV, median, minimum, maximum, and 95% CI. Geometric mean and geometric CV will be presented for C_{max} and AUCs only.

The effect of ALXN1840 on the bupropion PK will be assessed using a linear mixed-effect model (SAS PROC MIXED) with treatment condition, sequence, and period as fixed effects and participant nested within sequence as a random effect. The model will be fitted to the natural-log-transformed PK parameters C_{max} , AUC_{∞} and AUC_t for estimation of effects and construction of CIs for the test treatment (Treatment B: 150 mg bupropion + 60 mg ALXN1840) compared with the reference treatment (Treatment A: 150 mg bupropion). The within-participant CV for the corresponding PK parameters will be estimated using the mean squared error from the statistical model. Confidence intervals (90%) will be constructed for the least-squares geometric mean ratio (GMR) estimates between the test and reference treatments for above PK parameters using the natural log-transformed data. The GMR estimates and the associated 90% confidence limits will be exponentiated back to the original scale. These analyses will be repeated to assess the effect of ALXN1840 on hydroxybupropion PK.

Analyses of other PK data including, but not limited to PUF Mo may be conducted.

Pharmacodynamic data of ALXN1840 including, but not limited to, plasma total Cu, Cp, CpC, and potentially toxic Cu measured as LBC and PUF Cu and/or assessed via NCC/NCC corrected may be analyzed and reported.

Details of the PK/PD analyses will be described in the PK/PD data analysis plan or included in the SAP, which will be finalized before database lock.

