7.3. Study Treatments

Study treatments will be administered in each study period at the morning of Day 1 and all participants will receive 1 treatment in each study period. Study treatments are as follow

- Treatment A: One 150 mg bupropion HCl salt tablet (WELLBUTRIN SR 150) with 240 mL water (fasting).
- Treatment B: One 150 mg bupropion HCl salt tablet (WELLBUTRIN SR 150) + 4 × 15 mg ALXN1840 EC tablets with 240 mL water (fasting).

Any dose of ALXN1840 or bupropion greater than that specified in the protocol will be considered an overdose.

Study treatment administration data will be presented in a data listing for the safety set.

8. Safety Analysis

All safety analyses will be performed on the safety set.

Safety analyses will include an analysis of all AEs, ECGs, clinical laboratory data, physical examinations, and vital sign measurements using descriptive statistics. Summaries will be presented by treatment and overall, unless otherwise stated. Shift tables will be summarized with count and percentages of participants in each category. Percentages will be based on the number of participants with both non-missing baseline and relevant post-baseline results.

No inferential statistical analyses are planned for the safety parameters of this study.

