9.5. Pharmacokinetic Statistical Analysis

Plasma concentration data for total molybdenum, PUF molybdenum, bupropion and hydroxybupropion will be summarized separately for each scheduled sampling time using descriptive statistics. Plasma concentrations of total molybdenum, PUF molybdenum, bupropion and hydroxybupropion and time deviation data will be presented in a data listing by participant. Mean plasma concentration versus scheduled time profiles will be presented in figures on both linear and semilogarithmic scales. Individual plasma concentration versus actual time profiles will be presented similarly.

Pharmacokinetic parameters derived from plasma concentrations of total molybdenum, PUF molybdenum, bupropion and hydroxybupropion will be presented in data listings and summarized separately using the following descriptive statistics: N, n, arithmetic mean, SD, arithmetic CV, median, minimum, maximum, and 95% confidence interval (CI). Geometric mean and geometric CV will be presented for C_{max} and AUCs only.

The effect of ALXN1840 on bupropion and hydroxybupropion PK will be assessed using a linear mixed-effect model (SAS PROC MIXED) with treatment condition, sequence, and period as fixed effects and participant nested within sequence as a random effect. The model will be fitted to the natural-log-transformed PK parameters C_{max} , AUC_t, and AUC_∞ for estimation of effects and construction of CIs for the test treatment (Treatment B: 150 mg bupropion + 60 mg ALXN1840) compared with the reference treatment (Treatment A: 150 mg bupropion). The within-participant CV for the corresponding PK parameters will be estimated using the mean squared error from the statistical model. Confidence intervals (90%) will be constructed for the least-squares geometric mean ratio (GMR) estimates between the test and reference treatments for the indicated PK parameters using the natural log-transformed data. The GMR estimates and the associated 90% confidence limits will be exponentiated back to the original scale. The statistical results will also be graphically presented using a forest plot.

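### Does entering 150 mg of bupropion HCl salt for CL/F and Vd/F in SAP 9.4, with the assay's mass basis unstated, require a change to the plan?

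*SAP*

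**What the plan says.** SAP Section 9.4 lists the noncompartmental parameters and gives the doses that enter CL/F and Vd/F. For the perpetrator drug it states that an "equivalent molybdenum dose will be used to calculate total molybdenum" values, and it shows the molecular weights and the result, 13.31 mg. The next sentence covers the victim drug: "For bupropion, 150 mg dose will be used for the calculation". It gives no salt or base qualifier and no conversion.

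SAP Section 7.3 defines Treatment A as "One 150 mg bupropion HCl salt tablet (WELLBUTRIN SR 150) with 240 mL water (fasting". Treatment B uses the same tablet. The Protocol synopsis describes the substrate as "bupropion (bupropion hydrochloride [HCI], WELLBUTRIN SR), a sensitive CYP2B6 substrate, at a single dose of 150 mg". The 150 mg is therefore salt mass.

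SAP Section 9.1 provides for "measurement of plasma concentrations of total molybdenum, PUF molybdenum, bupropion and hydroxybupropion". Protocol Section 8.5 likewise names the analyte simply as bupropion. Neither document gives the basis on which the laboratory reports it.

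Under SAP Section 9.5, derived parameters are "summarized separately using the following descriptive statistics: N, n, arithmetic mean, SD, arithmetic CV, median, minimum, maximum, and 95% confidence interval". The mixed model in that section is fitted only to log Cmax, AUCt and AUC∞. Protocol Section 9.4.3.1 adds: "Details of the PK/PD analyses will be described in the PK/PD data analysis plan or included in the SAP".

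**The concern.** CL/F is a dose divided by an area under a concentration curve. If the numerator is salt mass and the denominator is built from free-base concentrations, the quotient is too large by the ratio of the two molecular weights. Vd/F carries the same factor.

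The SAP puts the dose on the analyte's basis for ALXN1840, with the arithmetic shown, and then enters a bare 150 mg for a drug that it calls a salt elsewhere. That looks like an oversight. The instruction is also unconditional, so an analyst who follows it literally would enter 150 mg even for a free-base assay.

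At stake are the absolute values of bupropion CL/F and Vd/F in the listings and summary tables. A shift common to both treatments would not show up in any comparison within the study. It would matter only to a reader comparing those absolute values with another source.

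**Working it through.** **Inputs from the documents.** Bupropion dose constant 150 mg (SAP 9.4); the 150 mg is HCl salt (SAP 7.3, Protocol 1.1); molybdenum 95.95 Da, ALXN1840 432.54 Da, dose 60 mg (SAP 9.4).

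**Inputs assumed.** Bupropion free base 239.74 g/mol and HCl 36.46 g/mol, so the salt is 276.20 g/mol. A base weight of 200 to 300 g/mol is carried alongside to show how far the answer depends on this.

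**Step 1: the plan's own conversion.** Equivalent dose = analyte weight / dosed-form weight × dose = 95.95 / 432.54 × 60 = 13.3098 mg, which rounds to the stated 13.31 mg. It reproduces.

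**Step 2: how the constant enters.** CL/F = D / AUC∞ and Vd/F = D / (λz × AUC∞). Both are linear in D, so a wrong basis multiplies both by (base + HCl) / base.

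**Step 3: size under each reading.**

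| Concentration basis | Assumed base weight (g/mol) | Matching dose (mg) | Effect of entering 150 mg |
|---|---|---|---|
| HCl-salt equivalent | any | 150 | 0% |
| Free base | 239.74 | 150 × 239.74/276.20 = 130.2 | 276.20/239.74 − 1 = +15.2% |
| Free base | 200 | 150 × 200/236.46 = 126.9 | 236.46/200 − 1 = +18.2% |
| Free base | 300 | 150 × 300/336.46 = 133.7 | 336.46/300 − 1 = +12.2% |

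**Step 4: what moves.** In the free-base case the mean, SD, median, minimum, maximum and 95% CI limits of CL/F and Vd/F all scale by one factor. The arithmetic CV does not, because SD and mean scale together.

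**Step 5: what does not move.**

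- Cmax, AUCt and AUC∞ contain no dose term. Their geometric mean ratios and 90% confidence intervals are therefore unaffected.
- Half-life is ln 2 / λz, with no dose term.
- The metabolite-to-parent ratios are quotients of Cmax or AUC, with no dose term.
- The Treatment B to A ratio of CL/F is (D/AUC_B) / (D/AUC_A) = AUC_A / AUC_B. The constant cancels. In simulated data for 32 participants the geometric mean ratio of CL/F was 0.8535 with 150 mg and 0.8535 with 130.2 mg.

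**Step 6: which results the study rests on.** Protocol Section 3 and SAP Sections 3.3.1 and 3.3.2 name Cmax, AUCt and AUC∞ as the pharmacokinetic endpoints. Protocol 9.4.3.1 does include CL/F and Vd/F in a list introduced as parameters calculated as endpoints, but neither that section nor SAP 9.5 models them. Neither document sets a criterion on their absolute values.

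**The case for a change.** The best case for a change is that it would be cheap and the instruction is definite. A pharmacokinetic constant fixed in advance should be unambiguous. The SAP shows its working for one drug and not for the other, and any free-base assay makes 150 mg too large whatever the exact molecular weight. If another document stated a free-base assay, it would sit awkwardly beside the SAP's 150 mg.

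The factual core of this stands: the basis is not stated, and under one reading two descriptive parameters would be overstated. The rest carries less weight.

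- The molybdenum conversion does not establish a general rule that was then broken. The laboratory measures an element that makes up about 22% of the dosed molecule (95.95/432.54), so some conversion was unavoidable. Salt against base is a labelling convention.
- The reporting basis belongs to the bioanalytical method, which is not among the documents, and the protocol allows analysis detail to sit in a separate PK/PD plan. Silence here does not mean that the point is unsettled.
- The reporting basis can also scale absolute Cmax and AUC. The same holds for the ratios in SAP 9.4, where "metabolite to parent ratios will be reported for" Cmax, AUCt and AUC∞, if those are taken on mass; the SAP does not say whether they are. That is a question about concentration units, separate from the 150 mg, and rewording the dose sentence alone would not answer it.

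**Conclusion.** No change to the plan follows. The 150 mg is salt mass and the concentration basis is unstated, but this is a missing label and not a demonstrated error: the constant is exactly right under one of the two readings. Under the other, absolute bupropion CL/F and Vd/F would be about 15% too high (12% to 18% across the assumed range of base weights), equally in both treatments. That figure rests on molecular weights outside the documents and on an assay basis that they do not reveal, so it is illustrative.

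The calculation as written is definite and reproducible. A pharmacokineticist working from the bioanalytical method can identify the basis and footnote the table, and a single multiplier would restate both parameters if needed. The primary and secondary endpoints, the geometric mean ratios with their 90% confidence intervals, and the comparison of CL/F between treatments are the same either way. It is a gap that analysts can fill sensibly, with no effect on what the study concludes about the interaction.

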9.5. Pharmacokinetic Statistical Analysis

Plasma concentration data for total molybdenum, PUF molybdenum, bupropion and hydroxybupropion will be summarized separately for each scheduled sampling time using descriptive statistics. Plasma concentrations of total molybdenum, PUF molybdenum, bupropion and hydroxybupropion and time deviation data will be presented in a data listing by participant. Mean plasma concentration versus scheduled time profiles will be presented in figures on both linear and semilogarithmic scales. Individual plasma concentration versus actual time profiles will be presented similarly.

Pharmacokinetic parameters derived from plasma concentrations of total molybdenum, PUF molybdenum, bupropion and hydroxybupropion will be presented in data listings and summarized separately using the following descriptive statistics: N, n, arithmetic mean, SD, arithmetic CV, median, minimum, maximum, and 95% confidence interval (CI). Geometric mean and geometric CV will be presented for C_{max} and AUCs only.

The effect of ALXN1840 on bupropion and hydroxybupropion PK will be assessed using a linear mixed-effect model (SAS PROC MIXED) with treatment condition, sequence, and period as fixed effects and participant nested within sequence as a random effect. The model will be fitted to the natural-log-transformed PK parameters C_{max} , AUC_t, and AUC_∞ for estimation of effects and construction of CIs for the test treatment (Treatment B: 150 mg bupropion + 60 mg ALXN1840) compared with the reference treatment (Treatment A: 150 mg bupropion). The within-participant CV for the corresponding PK parameters will be estimated using the mean squared error from the statistical model. Confidence intervals (90%) will be constructed for the least-squares geometric mean ratio (GMR) estimates between the test and reference treatments for the indicated PK parameters using the natural log-transformed data. The GMR estimates and the associated 90% confidence limits will be exponentiated back to the original scale. The statistical results will also be graphically presented using a forest plot.

9.6. Genetic Variant Analyses for CYP2B6

Participants with variant CYP2B6 alleles will be identified in the PK concentration and parameter listings, where applicable. Characterization of the potential impact of ALXN1840 on phenotypic CYP2B6 metabolism of bupropion to the formation of hydroxybupropion and genetic polymorphism on the between-participant variability of bupropion PK are exploratory assessments. Thus, this study does not specifically select target participants with a certain proportion of CYP2B6 genotypes. Depending on the distribution of CYP2B6 genotypes within treatments, the impact of ALXN1840 coadministration on bupropion and hydroxybupropion PK may be stratified by CYP2B6 genotypes to assess the potential impact of ALXN1840 on bupropion metabolism.

9.7. Pharmacodynamic Parameters

The following PD parameters will be calculated using noncompartmental methods for plasma total copper and PUF copper (measured and absolute change from baseline)

concentrations with Phoenix[®] WinNonlin[®] (Certara USA Inc., Princeton, New Jersey) Version 8.0 or higher or SAS Version 9.4 or higher (SAS Institute Inc., Cary, North Carolina), as applicable. Calculations will be based on the actual sampling times relative to the actual reference ALXN1840 dosing times recorded during the study.

- E_{max}: maximum observed PD concentration in plasma
- TE_{max} : time to reach maximum observed PD concentration in plasma
- AUEC_t: area under the effect versus time curve (AUEC) from time 0 to last quantifiable concentration time, calculated using the linear trapezoidal rule

Additional PD parameters may be calculated as necessary.

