 To determine the effect of ALXN1840 on the PK of hydroxybupropion, the major active metabolite of bupropion To determine the effect of ALXN1840 on the PK of plasma molybdenum (Mo) with the coadministration of bupropion To determine the safety and tolerability of ALXN1840, with the coadministration of bupropion 	 PK parameters of hydroxybupropion (C_{max}, AUC_t, and AUC_∞) with and without the coadministration of ALXN1840 PK parameters for plasma total Mo (C_{max}, AUC_t, and AUC_∞) with the coadministration of bupropion Safety assessed by incidence of treatment-emergent adverse events (TEAEs) and treatment-emergent serious adverse events (TESAEs), physical examination, vital signs measurements, clinical laboratory and 12-lead electrocardiogram (ECG) results

Abbreviations: AUC_{∞} = area under the plasma concentration versus time curve from time 0 to infinity; AUC_t = area under the plasma concentration versus time curve from time 0 to the last quantifiable concentration; C_{max} = maximum observed plasma concentration of the drug; CYP2B6 = Cytochrome P450 2B6; ECG = electrocardiogram; MO = molybdenum; PK = pharmacokinetics; TEAE = treatment-emergent adverse event; TESAE = treatment-emergent serious adverse event

Overall Design

This is a Phase 1, randomized, 2-period, 2-sequence, cross-over study designed to determine the effect of ALXN1840 on the metabolism of bupropion, a sensitive CYP2B6 substrate, in healthy male and female participants. The safety and tolerability of ALXN1840 will be determined along with ALXN1840 PK in plasma as measured via total Mo with the coadministration of bupropion.

Disclosure Statement: This is an open-label, 2-period, 2-sequence, cross-over study in healthy participants with randomization to 2 treatment sequences.

Number of Participants:

It is planned that approximately 52 participants will be enrolled and randomized at a single site.

Intervention Groups and Duration:

The study has a Screening Period (Day -28 to Day -2), two 11-day study periods (Day 1 to Day 11) with a minimum of 14 days between doses of bupropion, and an End of Study (EOS) Visit (Day 15 ± 2 days) after Period 2 dosing. Participants will report to the CRU on the day prior (Day -1) to both dosing periods.

In each study period, participants will receive one of the 2 treatments noted below:

- Treatment A: One 150 mg bupropion HCl salt tablet (WELLBUTRIN SR 150) with 240 mL water (fasting).

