 $^{^{\}circ}$ Participants are required to return to the CRU approximately Day 15 (\pm 2 days) following the final dose of study medication for an EOS evaluation. Participants may be asked or required to stay in the CRU between Periods 1 and 2, and/or before the EOS visit, for their own safety, and also to maintain the integrity of the conduct of the study. In the event of early termination/discontinuation (ET), the procedures listed at the EOS are performed prior to participant discharge.

d Hour 0 corresponds to the time of bupropion ± ALXN1840 administration. Unless stated otherwise, times listed are in relation to bupropion ± ALXN1840 dosing.

^e The nominal 336-hour sample for Period 1 is to be collected pre-dose in Period 2.

^f Parameters include age and sex. Race and ethnicity will be collected where permitted by local regulations.

^g A full physical examination will be performed at Screening, Check-in for each period, and at the end of the study or upon ET. A symptom-driven physical examination may be performed at other times, at the PI's discretion.

^h Randomization will occur before dosing.

¹ Each dose administration will be separated by at least 14 days between bupropion alone or in combination with ALXN1840 doses. There will be a minimum of 14 days between Day 1 of Period 1 and Day 1 of Period 2.

^j Samples for chemistry will be obtained following a fast of at least 6 hours at Screening, and at Check-in. In case of dropouts, rechecks, and post dose chemistry, fasting is not required (Section 10.2).

^k Only needed if claiming exemption from contraception requirement due to menopause.

Abbreviations: AE = adverse event; BMI = body mass index; C-I = Check-in; CRU = clinical research unit; ECG = electrocardiogram; EOS = End of Study; ET = Early Termination; FSH = follicle-stimulating hormone; HIV = human immunodeficiency virus; HR = heart rate; PI = Principal Investigator; PK = pharmacokinetics; S = Screening.

¹ Triplicate 12-lead ECG will be taken at screening, pre-dose, and at 4 hours post-dose (before lunch) on Day 1. ECGs will be conducted before PK blood sampling if these 2 events are scheduled to occur at the same time.

^m A single 12 mL sample will be retained for evaluation in the event of an unexpected safety finding; retained samples may be destroyed after completion of the clinical study report. The retained serum sample will only be collected pre-dose on Day 1 of Period 1.

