3.2. Schema

[figure not shown]

Figure 1:Study ALXN1840-HV-103 Schematic

Participants will be admitted on Day -1 of each period for Check in procedures. Eligible participants will be randomized on Day 1 immediately prior to dosing in Period 1.

Participants will receive treatment (A or B) based on randomization on Day 1 of each period. Blood samples for PK analysis of total molybdenum (as a measure of ALXN1840) and bupropion will be collected in each period on Day 1 at pre-dose, 1, 2, 3, 4, 5, 6, 8, 12 and 24 hours (Day 2) and then at 24 hour intervals on Days 3, 4, 5, 6, 7, 8, 9, 10, and Day 11. The nominal 336-hour sample for Period 1 will be collected pre-dose in Period 2. Participants will be discharged on Day 11 of each period a fter completion of all procedures and review of all safety data. The end of study visit (EOS) will occur on Day 15 \pm 2 of Period 2, with the collection of 336-hour PK sample for Period 2.

Participants may be asked or required to stay in the CRU between Periods 1 and 2, and/or before the EOS visit, for their own safety, and also to maintain the integrity of the conduct of the study.

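### The measured plasma total copper AUECt in SAP 9.7 has no common end time, so it scales with the date of the last sample; a fixed 0–240 h area would remove this

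*SAP*

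**What the plan says.** - SAP 9.7 lists one area parameter for copper, AUECt: "area under the effect versus time curve (AUEC) from time 0 to last quantifiable concentration time", by the linear trapezoidal rule. No fixed upper time is given.
- The time scale is actual: "Calculations will be based on the actual sampling times relative to the actual reference ALXN1840 dosing times recorded during the study".
- Two versions of each profile are planned, since the parameters apply to "plasma total copper and PUF copper (measured and absolute change from baseline".
- The copper data come from the PK samples (SAP 9.1), whose last scheduled times are "192, 216, 240, and 336 hours in each period".
- In Period 2 the last sample belongs to the "End of Study (EOS) Visit (Day 15 ± 2 days) after Period 2 dosing" (Protocol 1.1).
- In Period 1 it is the pre-dose sample of the next period: "The nominal 336-hour sample for Period 1 is to be collected pre-dose in Period 2" (Protocol 1.3 footnotes; SAP 3.2 agrees). The gap has a floor but no ceiling: "There will be a minimum of 14 days between Day 1 of Period 1 and Day 1 of Period 2".
- Protocol 8.5 and SAP 9.1 treat a PK sample as a deviation if it is off schedule by more than 10% or 30 minutes, whichever is less.
- SAP 9.2 sets all PUF copper values below the limit of quantification to zero for parameter calculation.
- SAP 9.8 summarises the copper parameters descriptively, with geometric means for the areas.

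**The concern.** For a drug that washes out, an area to the last quantifiable concentration is fairly insensitive to when the last visit happens, because little is left to add. Total copper is different. Protocol 8.3.6 speaks of normal copper levels in healthy participants, so a level exists before dosing and returns after it. If it is quantifiable throughout, which is an inference, the area ends at whatever time the last tube was drawn, and the measured area is close to level times duration.

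That time differs between participants and, by design, between periods. Treatment B is given in Period 2 in sequence AB and in Period 1 in sequence BA, so its window is 288–384 h in one sequence and 336 h or later in the other. Treatment A is the mirror image. A reported AUECt then mixes copper exposure with scheduling. A lost last sample adds a third end point, 240 h.

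Two smaller gaps sit beside this:

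- The PUF copper zeros after the last quantifiable value fall outside the integration window.
- The copper clock starts at the ALXN1840 dose, which does not exist in Treatment A. SAP 9.4 allows ALXN1840 or bupropion dose times for PK; SAP 9.7 does not.

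**Working it through.** **End times.** Hours = (Day − 1) × 24. Day 15 gives 336 h, which reproduces the plan's nominal time. Day 13 gives 288 h and Day 17 gives 384 h. Period 1: at least 14 × 24 = 336 h. Last sample missing: 240 h.

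**Measured version, flat copper, no drug effect.** The area is level × T, so the shift from 336 h is T/336 − 1.

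| Last sample (h) | Shift |
|---|---|
| 240 | −28.6% |
| 288 | −14.3% |
| 336 | 0 |
| 384 | +14.3% |

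If end times were uniform on 288–384 h, the CV from timing alone would be (96/√12)/336 = 8.2%.

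**Sequence difference within Treatment B.** Suppose, as an assumption, that Period 1 last samples spread evenly over 336–384 h (mean 360 h) and Period 2 last samples over 288–384 h (mean 336 h). The measured area in sequence BA then exceeds that in AB by 360/336 − 1 = 7.1% with no copper effect.

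**With a drug effect.** The documents give no copper effect size, direction or decay rate, so these are scenarios. Baseline is 1. The change is a rise that peaks at 4.54 h and declines with a chosen half-life, integrated by trapezoids on the SAP sampling grid. The 4.54 h and 51 h values are those given for total molybdenum in Protocol 4.3; 102 h and 168 h are slower alternatives.

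| Half-life | Drug effect on measured AUEC(0–336 h), peak rise 10% / 50% / 100% | Change-from-baseline area vs 336 h: ends at 240 / 288 / 384 h |
|---|---|---|
| 51 h | 2.3% / 11.6% / 23.3% | −3.2% / −1.3% / +1.1% |
| 102 h | 4.1% / 20.4% / 40.7% | −10.8% / −4.7% / +3.9% |
| 168 h | 5.5% / 27.6% / 55.2% | −16.4% / −7.5% / +6.4% |

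**When does timing exceed the effect on the measured version?** The effect is proportional to the peak rise. The ±14.3% limit equals it at a peak rise of 14.3/23.3 = 61% of baseline (51 h), 14.3/40.7 = 35% (102 h) or 14.3/55.2 = 26% (168 h). Below these, a 48 h shift is larger than the effect; above them it is smaller.

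**Baseline offset in the change version.** SAP 9.3 takes the pre-dose value as baseline. If it is off by an assumed 10%, a 48 h shift adds 0.10 × 48 = 4.8 baseline-hours. A 20% peak rise at 51 h gives 4.7% of 336 = 15.8 baseline-hours, so the offset contributes 4.8/15.8, about 30%.

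**Sample-time rule.** At 336 h the tolerance is min(33.6 h, 0.5 h) = 0.5 h, and 0.5/336 = 0.15%.

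**What is left at 240 h.** At a 51 h half-life from a 4.54 h peak: 2^(−(240 − 4.54)/51) = 4.1% of the peak.

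**The case against.** - *The change-from-baseline version is also planned.* This stands. Flat copper gives zero area there at any duration, and the realistic shifts are about 1% to 8%. It does not remove the problem from the measured version. Nor is the change version fully protected: a baseline offset accumulates with time. Its area can also be negative, in which case the planned geometric mean cannot be computed.
- *The 30-minute rule already fixes the time.* If it were kept, the end-time effect would be about 0.15%. But the rule only labels a sample as a deviation. The sample stays in, at its actual time, and the documents do not reconcile this tolerance with the ± 2 day visit window. Period 1 is also tied to the next dose, with no upper limit on the gap.
- *Participants may be kept in the unit between periods and before the final visit.* That may reduce the spread, but it is optional.
- *Nothing depends on it.* Largely true. Copper is in no objective or endpoint, the protocol says PD data may be analysed, and SAP 9.8 is descriptive, with concentrations by scheduled time and individual profiles. SAP 9.7 also allows additional PD parameters.
- *A reader might infer that AUECt reflects visit timing more than drug effect, or that scheduling biases the treatment contrast.* The documents support neither. The first depends on an effect size they do not give. On the second, with 26 participants planned per sequence each treatment is given equally often in each period, so a pure period difference in end time largely averages out of the treatment means and mainly adds spread. Unequal loss of late samples would weaken that balance.
- *PUF copper may reach the limit of quantification.* Correct: the argument about a level that is always measurable applies to total copper only. On the measured PUF scale, trailing zeros would add at most one descending trapezoid.

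**Conclusion.** The measured version of plasma total copper AUECt has no common end time and scales almost one for one with the time of the last sample: −14.3% to +14.3% across the Period 2 visit window and −28.6% if the area ends at 240 h, all against 336 h with flat copper. Within Treatment B the window differs by sequence. This rests on total copper being quantifiable in every sample and on the visit rules being used as written.

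The change-from-baseline version is affected much less: about ±1% at an assumed 51 h half-life and up to about 8% at 168 h, plus any baseline offset. Whether timing exceeds drug effect on the measured version cannot be settled from the documents. In the scenarios tried it does so only below a peak change of about 61% (51 h) or 26% (168 h) of baseline.

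Severity is low. The copper analysis is exploratory and descriptive, and the primary bupropion analysis is unaffected. The change is worth making because it is cheap and the rule as written gives values that are not comparable between participants.

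**What to change.** In SAP 9.7:

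1. Make AUEC(0–240 h) the area used for summaries of total and PUF copper, in both the measured and change versions. The 240 h sample is drawn on Day 11, in the unit, in both periods.
2. If a participant has no 240 h sample, set the fixed-window area to missing. Alternatively, report a time-averaged AUEC (area divided by actual duration) for everyone as a separate parameter. The two have different units and must not be mixed in one summary.
3. Include PUF copper values set to zero up to 240 h.
4. Use the bupropion dose time as time zero in Treatment A.
5. Reconcile the ± 2 day end-of-study window with the 30-minute sample tolerance in the protocol and SAP.

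The cost is SAP wording and one programming change, plus a protocol clarification for item 5. No new samples are needed. The downside is loss of the 240–336 h segment: the change-from-baseline area falls by about 3% at a 51 h half-life, and by about 11% to 16% at 102 to 168 h. If late copper change is of interest, AUECt can stay as a listed supplementary parameter with its end time shown.
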